An additional innovation in the current proposal is the utilization of a conceptual framework that is applicable to the RLTC placement transition for families. The conceptual model underlying the proposed study is the Stress Process Model for Residential Care (SPM-RC), developed by [name] and colleagues²⁰ and based on the widely used Stress Process Model (SPM) for dementia caregiving (Pearlin et al.).⁷¹ The SPM offers a multidimensional, theoretical framework for analyzing the occurrence of stress and outcomes in the caregiving career.^{71,72} The model incorporates an appreciation for the sociodemographic context of care (e.g., background characteristics of the caregiver and care recipient), care demands (functional, cognitive, and behavioral severity of dementia), subjective stress (caregivers' emotional appraisals of and reactions to care demands), resources (formal and informal support), and caregiver well-being (physical and psychological indicators of caregivers' global well-being). The major mechanism that helps to explain exacerbated stress is proliferation:⁷² as stress accumulates in primary stressor domains, this stress then "spreads" to life domains outside of the primary caregiving situation (i.e., secondary stressors) which then negatively influences global dimensions of dementia caregivers' mental or physical health. In the SPM, psychosocial or formal resources are hypothesized to stem the proliferation of stress, thereby limiting or preventing negative health outcomes.

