Prior efforts have successfully analyzed and tested the SPM-RC model (and several hypothesized relationships within it) that informs the RCTM.²⁰ We predict that the RCTM will act as a psychosocial resource for family members, operating on and producing beneficial outcomes in the key outcome domains identified by the SPM-RC. The RCTM topic areas are linked to stressors identified in the model, and its psychoeducational approach is designed to strengthen family caregiver self-efficacy in these same domains. As such, we hypothesize reductions in primary subjective stress and negative mental health outcomes on the part of family caregivers (Specific Aim 1); reductions in secondary role strains (Specific Aim 2); and reductions in residential care stress (Specific Aim 3). Related to the predicted outcomes, we have – innovatively, we believe – tailored our measurement strategy to capture outcomes most closely associated with RLTC placement alongside more general measures of stress and mental health. Prior research focusing on RLTC entry for dementia caregivers employ measures designed for at-home care situations (e.g., the Zarit Burden Interview).^{22,23,75} Similarly, many studies of caregiver stress following RLTC placement include pre- and post-placement measurements that often do not capture challenges specific to residential care admission for caregiving families (e.g., perceptions of staff support; perceived adjustment to the RTLC transition). The inclusion of such measures in the proposed study will help to advance understanding of how individualized psychoeducational and psychosocial support can enhance family caregivers adaptation to a relative's RLTC admission. Our embedded evaluation strategy described earlier likewise addresses this gap.

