3.0 Study Endpoints/Events/Outcomes

3.1 Primary Endpoint/Event/Outcome:

- The parent study's primary outcomes include reductions in family members' primary subjective stress and negative mental health outcomes.
- The administrative supplement's primary outcomes include changes in caregivers' mental health and caregiving stress before and during the COVID-19 pandemic.

3.2 Secondary Endpoint(s)/Event(s)/Outcome(s):

- Parent study's secondary outcomes include secondary role stressors, and residential care stress. Other variables include context of care, caregiver depressive symptoms, primary objective stressors and resources.
- The administrative supplement's secondary outcomes include AD/ADRD caregivers' and care recipients' COVID-19 related experiences and resilience during COVID-19 pandemic.

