Information about core questions is provided and information is tailored to respond to the needs of the caregiver and family and woven across the sessions. Among the questions often addressed include: How does RLTC placement affect the caregiver or other family members participating in the counseling session?; What are the constraints and reasons for the way dementia care is provided in RLTCs?; How can this care be optimized?; and How can the family caregiver's voice be heard when expressing the long-term care goals of the relative? Critical stressors identified during the intake interview, crisis situations, and adaptation issues are taken into account when individualizing a "curriculum" that uses conversation, presentations and online information and support.

- **Psycho-education:** Education on how dementia affects the brain and behavior, personality, and cognition is provided to explain the changes the relative is currently experiencing and may experience in the future. There is a focus on the biological basis for why these changes occur, emphasizing that they are not under the relative's control.
- **Promotion of communication:** The objective is to strengthen family members' skills in understanding other family members' perspectives and to establish positive and collaborative relationships with RLTC staff.⁴⁸ The Four Steps of Conflict Resolution and dementia-friendly activities designed to engage the PWML are included.
- **Problem solving:** Individual and family counseling sessions help caregivers divide potentially overwhelming problems into manageable components and direct the caregiver or other family members to formal/informal services available within the facility and in the outlying community (e.g., ombudsman).
- **Patient behavior management strategies:** Instruction and practice focuses on acquisition of skills and strategies to manage reactions to unpredictable behavior [as utilized in evidence-based interventions for dementia family caregivers such as the Savvy Caregiver Program as well as strategies provided by the Alzheimer's Association].⁵³⁻⁵⁵
- **Concrete planning:** Goals for care to optimize personal and socioemotional care assistance for relatives in RLTC are explored and strategies are developed to secure support for them from other family members and facility staff. These goals can also be made concrete in the facility's care plan for the relative in RLTC.⁶⁷ Follow-up allows for refinement of the care plan.

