-Study schedule: Months 3-44 (see Timeline below)

-Time for participants: approximately 45 minutes

Treatment/Intervention Period. Participants will be randomly assigned in a 1:1 ratio to receive either the RCTM intervention or a usual care control condition. The project biostatistician ([name]) will generate a random assignment schedule using a random number generator provided by the SAS analysis system. Treatment condition assignments generated by this program will be printed and individual caregiver assignment slips will be placed in sequentially numbered, sealed opaque envelopes. The next sealed envelope in

SOCIAL PROTOCOL (HRP-580)

PROTOCOL TITLE: The Residential Care Transition Module

VERSION DATE: 2/10/2022

the sequence will be opened at the time each individual participant is randomly assigned to his or her condition. The randomization schedule will be stratified by family member relationship (spouse vs. non-spouse) and time since the relative's admission (3 months or less vs. over three months) to ensure balance on these important predictors of caregiver outcomes. Cases will be randomized within variable-sized blocks that range from 6 to 10 participants. No research staff or investigator interacting with potential participants will have access to the random assignment schedule, and, because of the variable block sizes and the sealed assignment envelopes, no person with participant contact will be able to determine the next treatment assignment in the sequence. These procedures accomplish both random treatment assignment and treatment allocation concealment throughout the trial, and are consistent with the recommendations of the CONSORT statement (see <http://www.consort-statement.org/>). The RC will inform the ADRD caregiver of their randomization status as soon as possible following completion of the baseline interviews.

-Study schedule: Months 3-44 (see Figure below)

-Time for participants: approximately 10 minutes

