17.0 Statistical Considerations

17.1 Data Analysis Plan:

Analysis of Specific Aims 1-3

Data available at baseline, 4 months, 8 months, and 12 months will allow for individual growth curve models that examine change in ADRD caregiver outcomes.^{103,104} Multilevel analysis approaches are available that support growth curve modeling. In this context, growth curve modeling is an example of a 2-stage modeling process consisting of 1) a within-subjects model across time, and 2) a between-subjects model that incorporates caregiver and person with ADRD covariates.^{105,106} The primary independent variable in the proposed investigation consists of an indicator variable for random assignment into the RCTM treatment condition or the attention care control. [SAS (version 9.4) Proc Mixed¹⁰⁷] will be used to conduct these analyses, as it supports multilevel and growth curve modeling procedures.

Our proposed analyses will provide in-depth tests of Specific Aims 1 to 3 (i.e., rates of change in primary subjective stress, secondary role strains, residential care stress, and caregiver depressive symptoms) over a 12-month period. In one set of outcome evaluations, the baseline value will be included as a covariate, and time will be “centered” at 4-months post-baseline. This scales the intercept effect to be a main effect of RCTM group assignment and allows the RCTM treatment and the attention control groups to have different 4-, 8-, and 12-month change trajectories, or an RCTM treatment*time interaction effect. After establishing that the individual growth parameter estimates have significant variance around the mean trajectories of change in key dependent variables, an RCTM treatment vs. control group indicator will be added as the key independent variable to predict intercepts and rates of change in outcomes. Additional analyses will determine if covariates (e.g., context of care indicators, primary objective stressors, and resources) significantly vary across the RCTM treatment and control groups at baseline and over time via growth curve modeling procedures. If statistically significant variations between the RCTM treatment and control groups are found, initial status and rate of change parameters for these covariates will be included in all tests to provide further statistical control.

SOCIAL PROTOCOL (HRP-580)

PROTOCOL TITLE: The Residential Care Transition Module

VERSION DATE: 2/10/2022

Secondary Analyses

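### The Aim 1–3 tests may adjust for covariates' change after randomisation, chosen by significance test, which can bias the treatment effect

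*Combined protocol and SAP*

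**What the plan says.** Section 17.1 (Analysis of Specific Aims 1-3) first describes growth curve models with the arm indicator as the key predictor; in one set of models the baseline outcome is a covariate. It then adds a screening step. Covariates, with context of care, primary objective stressors and resources given as examples, are examined to see whether they "significantly vary across the RCTM treatment and control groups at baseline and over time via growth curve modeling procedures". The consequence follows: "If statistically significant variations between the RCTM treatment and control groups are found", then "initial status and rate of change parameters for these covariates will be included in all tests to provide further statistical control".

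The plan gives no significance level for the screen and no closed list of covariates. It does not say whether a difference at baseline, over time, or both is needed. No unadjusted or baseline-only analysis is named as primary. The Secondary Analyses paragraph has Aims 1a and 1b mirror the Aim 1–3 analyses, so the rule reaches them as well.

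Three other places bear on this:

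- Section 2.3 (Innovation) defines resources as formal and informal support, and treats psychosocial or formal resources as what checks the spread of stress.
- Section 4.1 says that counselling sessions "direct the caregiver or other family members to formal/informal services available within the facility and in the outlying community".
- Section 3.2, under secondary outcomes, adds: "Other variables include context of care, caregiver depressive symptoms, primary objective stressors and resources".

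**The concern.** Randomisation balances baseline covariates in expectation. A difference between arms that appears during follow-up is either chance or a consequence of assignment; it is not confounding that needs control. If the RCTM improves access to support, and support reduces stress, then holding the change in support constant takes out part of the effect that Aims 1–3 set out to test. If the covariate and the outcome share an unmeasured cause, the same adjustment can produce an apparent effect where none exists, in either direction.

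The trigger makes this worse, because it is most likely to select the covariates that the intervention has moved. The estimate would then no longer be the effect of being assigned to the RCTM. Even where the RCTM changes none of the candidates, the final model is chosen from post-randomisation data.

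The risk is not equal across covariates. It cannot arise for fixed background characteristics and is unlikely for functional or cognitive severity. It is possible for behavioural stressors and most plausible for resources.

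**Working it through.** **Inputs from the plan (Section 17.2).** 120 per arm with 10% loss gives 120 × 0.90 = 108 per arm. Alpha is .05/4 = .0125. Stated power is .87 at 0.50 SD and .80 at 0.46 SD.

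**Reproducing the plan's power.** The noncentrality is d × √(n/2): 0.50 × √54 = 3.674 and 0.46 × √54 = 3.380, with 214 degrees of freedom. Two-sided at .0125, the noncentral t gives 0.875 and 0.805, which agrees with the plan. One-sided testing (0.924, 0.873) or ignoring attrition (0.916, 0.857) does not agree. The power statement is sound and serves as the benchmark.

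**Assumptions (not in the documents).** Screening at .05 two-sided; the RCTM shifts the covariate's change by a = 0 to 0.5 SD; the within-arm slope or correlation between covariate change and outcome is b = 0.3 to 0.5.

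**What adjustment does.** If the covariate lies on the causal path, the adjusted coefficient estimates 0.50 − a × b. For a = 0.5 that is 0.50 − 0.5 × 0.3 = 0.35, down to 0.50 − 0.5 × 0.5 = 0.25. If the covariate only shares an unmeasured cause with the outcome, the absolute bias is a × b: 0.5 × 0.3 = 0.15, up to 0.5 × 0.5 = 0.25.

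**Rule applied, one follow-up, a difference at either point triggers entry** (4,000 simulated trials per scenario; ranges run from b = 0.3 to 0.5):

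| Covariate shift (SD) | Rule fires | Mean estimate, true 0.50 | Power | True null, shared cause: absolute bias | Type I error (nominal 1.25%) |
|---|---|---|---|---|---|
| 0.2 | 35% | 0.47–0.44 | 0.83–0.81 | 0.03–0.06 | 1.8–2.4% |
| 0.3 | 61–62% | 0.43–0.39 | 0.76–0.72 | 0.07–0.12 | 2.6–7.0% |
| 0.5 | 96% | 0.35–0.25 | 0.54–0.33 | 0.15–0.25 | 8.4–31% |

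Power without the rule is 0.87–0.88. With no shift, the mean estimate stays at 0.50. Repeat runs agreed within simulation error, though the lower ends of the type I ranges moved somewhat (1.3% at a shift of 0.2, 7.5% at 0.5). A separate simulation with a simpler trigger (one test on the covariate summary) at a = 0.5, b = 0.4 gave 0.30 SD and power 0.42, as expected from 0.50 − 0.5 × 0.4.

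**Same model, differences at both points required.** The rule fires in at most 5% of trials; the estimate is 0.49–0.50, power 0.85–0.88 and type I error 1.2–2.6%.

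**Four waves (months 0, 4, 8, 12), either point triggers.** This is closer to the planned growth curves. It uses individual slopes and further assumes linear effects, an intercept share of variance of 0.6 and an SD of 12-month change of 0.7 (3,000 trials per scenario). Power without the rule is about 0.80 here.

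| Shift at 12 months (SD) | Mean estimate | Power | Null bias | Type I error |
|---|---|---|---|---|
| 0.3 | 0.47–0.45 | 0.72–0.69 | 0.03–0.05 | 1.3–1.5% |
| 0.5 | 0.44–0.39 | 0.64–0.54 | 0.07–0.11 | 2.1–4.7% |

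The harm is smaller because an estimated covariate slope carries measurement error.

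**Entry by chance when the RCTM changes nothing.** For k covariates with independent tests, the chance that at least one enters is 1 − 0.95^(2k) if either point triggers: 26%, 40% and 64% for k = 3, 5 and 10. If both are required it is 1 − (1 − 0.0025)^k: 0.7%, 1.2% and 2.5%. The number of covariates is assumed.

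**Minor point, precision only.** Section 5.2 stratifies randomisation by relationship and time since admission "to ensure balance on these important predictors of caregiver outcomes", but the factors are not named as model terms. If they explain 5–10% of residual variance (assumed), including them multiplies the standard error by √0.95 to √0.90, a cut of 2.5–5.1%. Power at 0.46 SD rises from 0.805 to 0.828–0.851. Omitting them does not bias the effect.

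**The case against.** The strongest reply is that nothing in the documents shows that the RCTM changes a screened covariate. Section 2.3 says "We predict that the RCTM will act as a psychosocial resource for family members", which describes the intervention itself as a resource; it does not predict a change in measured resources, and neither resources nor objective stressors are among the hypothesised outcomes. Under Usual Care in Section 5.2, controls who seek help also receive information and referral, which narrows any difference in service use. The behaviour training in Section 4.1 is aimed at managing reactions, so an effect on the care demand itself is less direct. All this stands and makes large shifts less likely, but it does not rule out an effect on resources.

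On size, a 0.5 SD shift equals the effect the trial is powered to find on its main outcomes, and the 31% type I error needs an extreme combination of assumptions. With correlations of 0.1–0.2 and shifts of 0.1–0.3 SD, the estimate is 0.46–0.50, power 0.79–0.88 and type I error about 1–2%. That also stands. The four-wave results and the smaller shifts are the better guide.

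On wording, requiring differences at baseline and over time together nearly removes the problem. The sentence that sets the consequence does not impose that requirement, however. The covariate step is also introduced as additional analysis, so simpler estimates would probably exist; but applying the adjustment to all tests leaves no simpler analysis protected as primary.

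**Conclusion.** The concern holds. The defect is in a stated rule: followed as written, it can put post-randomisation covariate change into every Aim 1–3 test. The bias is conditional on the RCTM changing a screened covariate that is related to the outcome, and on a difference at one point being enough to trigger entry. Under those conditions, a 0.3–0.5 SD shift lowers a true 0.50 SD effect to roughly 0.47–0.39 SD in the four-wave model and 0.43–0.25 SD in the single-follow-up model, with a clear loss of power in both. A shared unmeasured cause could instead raise the type I error above .0125. These sizes rest on assumed shifts, correlations and screening level, so confidence in any one figure is moderate. That the final model is not fixed in advance does not depend on those assumptions. The rule should be changed before the treatment-effect analysis; the stratification point is minor.

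**What to change.** Delete the significance-triggered rule. In every Aim 1–3 model, and in the Aim 1a and 1b models that mirror them, pre-specify:

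- the baseline value of the outcome;
- both randomisation stratification factors;
- if wanted, a short fixed list of other covariates measured at baseline only.

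State that no post-randomisation covariate or covariate slope enters the models that estimate the treatment effect. Use change in stressors and resources only in the mediation models already planned under Secondary Analyses in Section 17.1.

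The cost is a change of wording, with no new data. Chance baseline imbalances outside the fixed list would be handled in a sensitivity analysis and not in the primary model. Because this version is dated February 2022 and parent follow-up was planned through Month 55 of a project that began in June 2016, the amendment should record its date and whether anyone had seen outcome results by arm.

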In addition to analyses of secondary Aims 1a and 1b (which will mirror the Specific Aims 1-3 analyses described above), empirical treatment fidelity data on variations in use of RCTM (e.g., frequency and duration of counseling sessions) will be included in growth curve models as a series of post-hoc Specific Aims 1, 2, and 3 analyses. These analyses will explore the effects of variations in RCTM utilization on the outcomes hypothesized above. [A series of mediational models will also be tested examining some of the hypothesized pathways of the SPM-RC as described in the conceptualization of the proposed project (e.g., whether RCTM assignment mediates the empirical relationships between care-related stressors and more global psychological and emotional outcomes on the part of family caregivers). As detailed by Selig and Preacher and other methodologists, mediational models appropriate for longitudinal data will be utilized.¹⁰⁸ These analyses will explore the empirical mechanisms that explain RCTM's efficacy or lack thereof.]

Specific Aim 4 Analyses

Specific Aim 4 analyses will primarily focus on thematic content analysis of open-ended data to examine RCTM utility and mechanisms of benefit. Systematic reading and rereading of qualitative content and hand coding of a significant proportion of this content is necessary in order to develop an understanding of meanings in their conversational or observational contexts.^{109,110} Specifically, the PI, [name] (Co-Investigator) and the research assistants will independently develop coding categories together with descriptors (via hand-coding and NVivo) and will develop a shared coding scheme that will reflect the primary categories of the transcription. Through repetition of this procedure, a consensus perspective on appropriate coding categories and themes will be modified and developed. These themes will provide insights as to the RCTM's implementation and use (i.e., treatment fidelity/process evaluation) and mechanisms of benefit (i.e., semi-structured interview embedded component).

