Additional mixed methods analyses^{63,64} will take place to complete Specific Aim 4. The thematic codes and categories of the post-RCT embedded component will be cross-tabulated with the empirical data from the RCT to determine whether the findings diverge, converge, or highlight pathways toward additional questions and analysis.⁶⁴ Findings that diverge will be treated as “interpretive opportunities” to either demonstrate that no true discrepancy in efficacy exists or to propose the phenomenon that explains the apparent discrepancy.¹¹⁵ Specifically, empirical outcome data of the RCT will be sorted according to the qualitative themes that emerge across the two subgroups of the embedded semi-structured interview component (e.g., increased or decreased rates of change in care-related strain). This integration will provide empirical context for ADRD caregivers’ statements regarding why the RCTM is perceived to work or not, respectively.^{64,116} The comparative, mixed method analysis approach may also suggest that those who reported greater increases in subjective stress during RCTM use may indicate certain themes more often or may use RCTM differently than ADRD caregivers who report greater decreases in care-related strain.

The post-intervention interviews will help explain mechanisms of benefit based on the questions of “why” and “how” that are implicit in qualitative data. While empirical analyses such as mediational models might provide some suggestion as to why the RCTM exerts benefits, utilizing qualitative data is a more comprehensive approach by allowing intervention participants to describe, in their own words and experiences with the RCTM, why the psychosocial support provided helped families adapt to the RLTC transition. Such an approach may also identify domains untapped in empirical measurement. This certainly occurred in the pilot evaluation of RCTM efficacy,¹¹⁷ and is largely why a mixed methods design for this larger-scale evaluation was selected. Also, the qualitative data that emerge from the post-RCTM interviews may suggest additional secondary analyses of the empirical data that could test possible mediators or path analyses (see above). In this regard, the mixed methods approach is advantageous for the proposed project.

Planned Interim Analyses

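### The one mediation model the plan spells out makes randomised assignment the mediator, an order that cannot show how the RCTM works

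*Combined protocol and SAP*

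**What the plan says.** Section 17.1, under Secondary Analyses, states: "A series of mediational models will also be tested examining some of the hypothesized pathways of the SPM-RC". The single illustration is "whether RCTM assignment mediates the empirical relationships between care-related stressors and more global psychological and emotional outcomes". The purpose follows: "These analyses will explore the empirical mechanisms that explain RCTM's efficacy or lack thereof". The paragraph cites longitudinal mediation methods but names no mediator, time point or other model. The Specific Aim 4 text mentions possible mediators only in general terms.

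Three other parts of the document fix the place of assignment in the causal order:

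- Section 5.2 (Treatment/Intervention Period): the biostatistician "will generate a random assignment schedule using a random number generator provided by the SAS analysis system", 1:1, stratified by spouse or non-spouse and by time since admission. No stressor is a stratification factor.
- Section 17.1 (Specific Aims 1–3): "The primary independent variable in the proposed investigation consists of an indicator variable for random assignment".
- Section 2.3 (conceptual model): the RCTM is described as "operating on and producing beneficial outcomes in the key outcome domains identified by the SPM-RC", partly by strengthening self-efficacy, and in the underlying stress process model "psychosocial or formal resources are hypothesized to stem the proliferation of stress".

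**The concern.** A mediator has to be caused by the exposure and has to precede the outcome. The example asks for stressor → assignment → outcome, although assignment is produced by a random number generator. The plan's own theory points to one of two different structures. One is assignment → stressor, resource or self-efficacy → outcome. The other is the RCTM weakening the link from stressor to outcome, which is moderation.

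The quantitative explanation of why the RCTM did or did not work is what is at stake. An analyst who follows the only worked example could report no mechanism where there is one, or report mediation where the stressor plays no part.

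**Working it through.** The plan states no figure here, so there is none to reproduce. The argument is structural; the simulation only shows its size.

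**Inputs from the plan.** Enrolment is 240 with 10% loss (Section 17.2): 240 × 0.90 = 216, or 108 per arm, randomised 1:1.

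**Assumptions, not in the plan.** Stressors are standardised, with baseline-to-follow-up correlation 0.5. The RCTM lowers the follow-up stressor by δ = 0, 0.25 or 0.5 SD. The slope of outcome on follow-up stressor is 0.5, or 0 for no mechanism. The direct effect of the RCTM on the outcome is d = 0, 0.25 or 0.5 SD.

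**Model as written.** Regress assignment R on the stressor (path a), then the outcome on R and the stressor (path b, the coefficient of R). The indirect effect is a × b, and a trial counts as positive if both paths have p < .05.

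*Timing 1, baseline stressor.* Randomisation makes Cov(stressor, R) = 0, so a = 0 and a × b = 0 whatever b is. A positive result needs a chance imbalance in a.

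*Timing 2, follow-up stressor.* With 1:1 allocation Var(R) = 0.25, so Cov(stressor, R) = −0.25δ. For δ = 0.5:

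- Var(stressor) = 1 + 0.5² × 0.25 = 1.0625
- a = −(0.25 × 0.5)/1.0625 = −0.118, which is the RCTM's effect on the stressor read backwards
- b = −d, the direct effect alone, because the stressor is held fixed
- a × b = 0.118 × d: 0 for d = 0, 0.029 for d = 0.25, 0.059 for d = 0.5

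The slope from stressor to outcome does not enter. The quantity tested therefore tracks the part of the benefit that bypasses the stressor. In the correct order the indirect effect is −δ × slope = −0.5 × 0.5 = −0.25, or 0 if the slope is 0.

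**Correct order, for comparison.** Regress the follow-up stressor on R and baseline stressor; then the outcome on follow-up stressor, R and baseline stressor.

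**Simulation, 4,000 trials per scenario, percentage positive:**

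| Scenario | As written, follow-up stressor | Correct order |
|---|---|---|
| δ 0.5, slope 0.5, d 0 (all benefit through the stressor) | 5% | 99% |
| δ 0.5, slope 0, d 0.5 (none through the stressor) | 90% | 5% |
| δ 0.5, slope 0, d 0.25 (none through the stressor) | 40% | 5% |
| δ 0.5, slope 0.5, d 0.25 (both) | 51% | 99% |
| δ 0.5, slope 0.5, d 0.5 (both) | 94% | 99% |

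With a baseline stressor, the model as written was positive in 0.3% to 5.5% of trials over RCTM effects of 0 to 0.5 SD, with mean indirect effect 0.000.

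The two rows with both paths depend on how the outcome's residual variance is set. They use an outcome residual scaled to give roughly unit variance; an unscaled residual SD of 1 gives about 41% and 90% as written. The other rows do not move materially.

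**The case against.** The strongest reply is that this is one loosely worded example in an exploratory series governed by the conceptual model, which already implies workable orders. The word chosen may be a slip for moderation. Other models in the series could be correctly ordered, and the Aim 4 text gives mediation a small part: "mediational models might provide some suggestion as to why the RCTM exerts benefits", with qualitative data treated as the fuller source.

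Most of that is fair, and it limits the consequences. It does not rescue the example. This is the only mediation model written out, and citing longitudinal methods does not change which variable is named as mediator. Moderation is a different model, so the text would need changing under that reading too.

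Two further points stand. The simulation uses a simple two-regression test and assumed effects, whereas the plan promises longitudinal models without naming a test; the percentages are illustrative and the causal-order argument does not need them. The corrected model is also not powerful for small effects: if the RCTM lowers the stressor by only 0.25 SD (slope 0.5), it is positive in about 55% of trials, against 99% at 0.5 SD.

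**Conclusion.** The concern holds: the example is wrong as written. With baseline stressors its indirect effect is zero by design. With later stressors it reverses cause and effect and responds to the direct effect rather than to the mechanism. That conclusion rests only on assignment being randomised and on the order of measurement. The sizes (about 5% against 99% when the mechanism is real, about 90% against 5% when it is absent) rest on the assumed effects and on 216 analysed caregivers.

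The reach is limited to exploratory secondary results on mechanism. The growth-curve comparisons for Aims 1–3, the .0125 significance level, the sample size and the qualitative work for Aim 4 are unaffected. It should be corrected, but it does not threaten the trial's main conclusions.

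**What to change.** Replace the example in Section 17.1 with one or both of the following, according to what was meant:

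1. **Mediation.** Assignment is the exposure. The mediator is a named stressor, resource or self-efficacy measure at a stated post-baseline visit, for example 4 months. The dependent variable is an outcome at a later visit, for example 8 or 12 months. Adjust for baseline mediator, baseline outcome and a prespecified set of mediator–outcome confounders. The longitudinal mediation methods already cited can stay.
2. **Moderation.** If buffering was intended, test an assignment-by-baseline-stressor interaction on the outcome and call it moderation.

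Reversing the order, or relabelling the test as moderation, is what repairs the error. Naming variables, visits and confounders is good practice that keeps the repaired analysis from being chosen after the fact.

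The cost is analysis-plan wording; the baseline, 4-, 8- and 12-month surveys already supply the ordering. Confounders must come from what those surveys measured, for example the context-of-care, objective-stressor and resource covariates listed in Section 17.1. The remaining weakness is that the mediator is not randomised, so option 1 assumes no unmeasured mediator–outcome confounding. In the same simulation with no true mechanism (δ 0.5, slope 0, d 0.5), a confounder with path 0.3 to both mediator and outcome produced false mediation in 32% of trials when omitted and about 5% when adjusted for. Option 1 should therefore be reported as exploratory, with a sensitivity analysis for unmeasured confounding.
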